13.3.2 Photopic Monocular DCNVA

Phase I/Pilot subjects will be excluded from the analysis of this endpoint.

Photopic monocular DCNVA (logMAR) at 40 cm in first eyes at Post-Operative Visit 4 (Day 120 to 180 after second eye IOL implantation) will be summarized using continuous summary statistics in logMAR units by treatment assignment for the mITT Set.

If there are missing mITT Set monocular DCNVA data in first eyes at Post-Operative Visit 4 (Day 120 to 180 after second eye IOL implantation), then missing data will be imputed using the MCMC multiple imputation method. A total of 30 imputation datasets will be created. After imputation of missing data, the statistical hypotheses will be tested using an ANCOVA model with treatment and site as fixed factors by imputation.

SAS® code for the MCMC multiple imputation:

```
PROC MI DATA=indata OUT=mcmc NIMPUTE=30 SEED= 1091148178;  
  BY trt;  
  MCMC INITIAL=EM;  
  VAR V3 V4;  
  RUN;
```

where

- trt = treatment
- v3 = actual value at Visit 3A
- v4 = actual value at Post-Operative Visit 4 (Day 120 to 180 after second eye IOL implantation)

An overall p-value resulting from the multiple imputation method will be estimated. The treatment effect (LS mean for Test group IOL VA minus LS mean Control group IOL VA) in logMAR units and a two-sided 95% CI will be provided. If the p-value from the multiple imputation analysis is less than or equal to 0.05 and the treatment effect is less than or equal to -0.10 (i.e., the Test lens mean logMAR VA is at least 0.10 less than the mean for the control), then it will be concluded that the Test IOL is statistically and clinically successful (i.e., superior to the Control IOL) in this outcome.

The previous continuous summary statistics will also be provided for the PP Set. However, superiority will not be evaluated with the PP Set, and statistical success will not depend upon the results of the PP analysis.

As a sensitivity analysis, observed DCNVA (logMAR) at 40 cm in first eyes at Post-Operative Visit 4 (Day 120 to 180 after second eye IOL implantation) will be compared between treatment groups using an ANCOVA model with treatment and site as fixed factors. The treatment effect (LS mean for Test group IOL VA minus LS mean Control group IOL VA) in logMAR units and a two-sided 95% CI will be provided. The analysis will be for the ITT set.

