### **11.1.7 Unscheduled Visit(s)**

Additional visits may be scheduled, as necessary, to ensure the safety and well-being of subjects. All additional examinations should be fully documented in the source documents and on Unscheduled Visit CRFs, as appropriate. Visits intended to fulfill scheduled visit requirements that fall outside the designated scheduled visit window will be collected and transcribed to the appropriate visit CRF.

If a subject is seen for multiple visits during a given visit timeframe, the data from the visit that is intended to meet the protocol requirements for the scheduled visit will be captured on the visit CRF. Where such a determination cannot be made, the first visit within the scheduled visit interval will be used for completion of the protocol required scheduled visit CRF. Data from any additional visits within a scheduled visit interval will be captured on an Unscheduled Visit CRF.

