9.5 Visit Window

For analysis of data by visit, only in-window visit data will be included in the analysis of a scheduled visit's data. If a scheduled visit is completed outside of the prescribed visit window, then the visit and its window will be handled as follows:

- The out-of-window scheduled visit will be reclassified as an interim (unscheduled) visit.
- If one or more unscheduled visits occurred in the window, then the unscheduled visit that occurred closest to the center of the visit window will be reclassified as the in-window (scheduled) visit.
- If two unscheduled visits occurred in the visit window, are the closest visits to its center, and are equidistant from its center, then the later of the two visits will be reclassified as the in-window (scheduled) visit.

9.6 logMAR Calculation

The following effectiveness data will be assessed as letters read correctly (letters correct) or as count fingers (CF), hand motion (HM), light perception (LP), or no light perception (NLP):

- Photopic monocular/binocular UCDVA
- Photopic monocular/binocular BCDVA
- Photopic monocular/binocular UCNVA
- Photopic monocular/binocular DCNVA
- Mesopic monocular/binocular DCNVA
- Photopic monocular/binocular UCIVA
- Photopic monocular/binocular DCIVA
- Mesopic monocular/binocular DCIVA
- Binocular BCDVA Defocus Curves
- Photopic monocular BCDVA (simulated astigmatism)
- Photopic monocular DCNVA (simulated astigmatism)
- Photopic monocular DCIVA (simulated astigmatism)

The logMAR VA for the data listed above will be computed as follows for subjects who can read at least one letter.

$$\text{logMAR VA} = 1.70 - (0.02 \times \text{letters read correctly})$$

Subjects who cannot read any letters but who can count fingers will be assigned a logMAR VA value of 2.00. Subjects who cannot read any letters but who can perceive hand motion will be assigned a logMAR VA value of 2.30. Subjects who cannot perceive hand motion will be assigned a logMAR VA value of missing.

For UCDVA and BCDVA data, logMAR score will be captured in the Electronic Data Capture (EDC) database. The scores will not be pulled from EDC database directly.

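### An out-of-window Visit 4 near or intermediate acuity is set aside and imputed from Visit 3A alone, and no planned comparison uses the measured value

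*SAP*

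**What the plan says.** **Collection.** Protocol 11.1.7 provides that visits meant to meet the schedule but which "fall outside the designated scheduled visit window will be collected and transcribed to the appropriate visit CRF". Protocol 11.1.8 calls a visit missed only if the subject cannot be seen before the next visit range opens. Visit 4 closes on Day 180 and Visit 5 opens on Day 330, so an examination on Days 181 to 329 is still a Visit 4 for collection purposes.

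**Window rule.** SAP 9.5, like Protocol 13.6.4, states that "only in-window visit data will be included in the analysis" of a scheduled visit. It continues: "The out-of-window scheduled visit will be reclassified as an interim (unscheduled) visit". There is one route back: if unscheduled visits occurred in the window, "the unscheduled visit that occurred closest to the center of the visit window will be reclassified as the in-window (scheduled) visit".

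**Imputation.** If first-eye Visit 4 DCNVA is missing in the mITT Set, "then missing data will be imputed using the MCMC multiple imputation method. A total of 30 imputation datasets will be created". The PROC MI code runs by treatment with `VAR V3 V4`, where "v3 = actual value at Visit 3A". SAP 13.3.3 applies the same method to DCIVA with another seed. First-eye DCNVA and DCIVA at Visit 5 are collected and are secondary endpoints (SAP 3.2.4), but they are not in the model.

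**Sensitivity analysis.** SAP 13.3.2 plans an ANCOVA on observed Visit 4 values in the ITT Set. SAP 9.5 governs what counts as a Visit 4 value there too.

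**COVID-19.** SAP 9.2 says COVID-related missing data or visits are not imputed. SAP 13.3.2 imputes missing mITT data without that exception.

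**The concern.** The plan has a direct measurement of the endpoint, taken at a visit intended as Visit 4, and replaces it with draws predicted from a measurement made 30 to 60 days after the first surgery. Success on DCNVA and DCIVA needs both p of at most 0.05 and a point estimate that reaches a threshold. A small shift in the estimate can therefore decide the outcome when the true difference is near the threshold. If subjects who attend late or early differ in acuity in a way that Visit 3A does not capture, the imputed values are biased. No planned analysis would show it, because the only sensitivity analysis excludes the same measurements.

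**Working it through.** **1. One case traced.** Take, for illustration, a subject seen for Visit 4 on Day 185, with no unscheduled acuity inside Day 120 to 180.
- Protocol 11.1.7: the acuity goes on the Visit 4 CRF.
- Protocol 11.1.8: the visit is not missed, since Day 185 precedes Day 330.
- SAP 9.5: it becomes an unscheduled visit.
- SAP 13.3.2 and 13.3.3: Visit 4 is missing and is imputed from Visit 3A.
- Observed-data sensitivity analysis: the subject is not included.

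**2. The plan's own figures (SAP 6.4: SD 0.15, 276 Test, 138 Control).** SE = 0.15 × √(1/276 + 1/138) = 0.01564. The probability that the observed difference is at most -0.10 is Φ((|true| - 0.10)/SE):
- true -0.12: Φ(0.02/0.01564) = 89.95% (stated 89%)
- true -0.13: 97.2% (stated 97%)
- true -0.14: 99.5% (stated 99%)

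Power to detect -0.10 is above 99.9% (stated 99%). The plan's figures reproduce, and none is disputed here.

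**3. Precision.** Let m be the share of Visit 4 values imputed and R² the variance of Visit 4 explained by the predictors. Then SE ≈ 0.01564 × √[(1 - mR²)/(1 - m)]. With a common between-visit correlation ρ, R² = ρ² for Visit 3A alone and 2ρ²/(1 + ρ) for Visit 3A plus Visit 5. At true -0.12:
- m = 10%, ρ = 0.5: R² = 0.25 gives SE 0.01628 and 89.0%; R² = 0.333 gives SE 0.01621 and 89.1%.
- m = 15%, ρ = 0.5: 88.5% against 88.7%.

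Superiority power stays above 99.9% throughout. Precision is not the issue.

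**4. Bias.** Simulation with 4000 runs and true difference -0.12. Assumptions not in the documents:
- In Test, the log-odds of being out of window rise by 1 per SD of worse Visit 4 acuity (9.7% out of window).
- In Control, 10% are out of window at random.
- The measured late value correlates 0.9 with the in-window value.
- Missing values are filled by regression prediction within arm.

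| ρ | Visit 3A only | Visit 3A + Visit 5 | Measured late value used |
|---|---|---|---|
| 0.5 | -0.1302 | -0.1291 | -0.1213 |
| 0.7 | -0.1270 | -0.1259 | -0.1211 |
| 0.8 | -0.1251 | -0.1241 | -0.1213 |

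The bias with Visit 3A only is 0.0102, 0.0070 and 0.0051. As a check, it should scale with 1 - R²: 0.0102/0.75 = 0.0136; 0.0136 × 0.51 = 0.0069; 0.0136 × 0.36 = 0.0049. This agrees.

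Adding Visit 5 removes 0.0011/0.0102 = 11%, 0.0011/0.0070 = 16% and 0.0010/0.0051 = 20% of the bias. Using the measured value removes 87%, 84% and 75%. At a 5% out-of-window rate the bias with Visit 3A only is 0.003 to 0.005. With 10% random lateness in both arms, all three approaches return -0.120.

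**5. Effect at the threshold.** If the true difference equals the criterion, the chance of meeting it is 50% without bias. With a bias of 0.0051 it is Φ(0.0051/0.01564) = 63%, and with 0.0102 it is Φ(0.0102/0.01564) = 74%, ignoring the small rise in SE.

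**The case against.** The window rule is prespecified and keeps the endpoint at Day 120 to 180. Without a limit, using recorded values could admit acuities months late. That stands, and the fix below sets a bound.

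A reader might infer that the measurement is lost. It is not: it remains as unscheduled data in the listings, and Protocol 13.6.4 plans to report days outside the window where unscheduled data are summarized. An in-window unscheduled visit can also stand in, if acuity was measured there. BCDVA is not imputed at all, so the replacement concerns DCNVA and DCIVA only. For COVID-related visits, SAP 9.2 says there is no imputation, so replacement there is not established.

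A reader might also infer that leaving out Visit 5 is the main fault, because Visit 5 predicts Visit 4 better. The documents do not support this. Visit 4 falls 127 to 210 days after the first surgery (7 + 120 to 30 + 180), so Visit 3A precedes it by 67 to 180 days. Visit 5 follows it by 150 to 300 days (330 - 180 to 420 - 120). Visit 3A is usually nearer, and a capsulotomy may come between Visits 4 and 5. Subjects lost before Visit 5 have no such value. Adding Visit 5 moves the simulated estimate by only about 0.001 logMAR.

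Finally, the bias depends on lateness being related to acuity in one arm. A similar relation in both arms would largely cancel in the difference.

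**Conclusion.** The gap is real but small. For monocular DCNVA and DCIVA, a recorded out-of-window Visit 4 value is replaced by imputation from Visit 3A alone, and no planned comparison uses the measurement. Random lateness gives no bias. Acuity-related lateness in one arm gives about 0.005 to 0.010 logMAR at an assumed 10% out-of-window rate, which is 5% to 10% of a 0.10 criterion. The direction favours Test if it is the worse Test eyes that are out of window, and reverses if it is the better ones. The documents state neither the out-of-window rate nor the between-visit correlations; the 10% allowance in SAP 6.7 is for losses.

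The documents do not support a claim that the primary tests lose meaningful power or that the superiority conclusion is in doubt. The point counts only if an estimate lands near its criterion. That criterion is itself inconsistent for DCNVA (-0.20 in Protocol 13.5.3.2, -0.10 in SAP 13.3.2), which is a separate matter to reconcile.

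**What to change.** 1. Prespecify one sensitivity analysis for each of DCNVA and DCIVA that uses the recorded out-of-window Visit 4 value in place of an imputed one. State a limit, such as before the Visit 5 window opens at Day 330, and report days outside the window by arm. This step recovers most of the bias.
2. Add Visit 5 and the out-of-window Visit 4 value to PROC MI as auxiliary variables. Visit 5 alone helps modestly, and not for subjects lost before it. Few subjects will have both an in-window and an out-of-window Visit 4 value, so the data will barely identify their covariance. The SAP should say how that is handled; item 1 remains the dependable use of the measurement.
3. Reconcile SAP 9.2 with SAP 13.3.2: say whether COVID-related missing Visit 4 values are imputed in the primary analysis.

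The cost is a small code change and one extra run per endpoint. Item 2 also makes the imputation wait for Visit 5 data. The SAP is written for the final study report, when those data exist. Its contents list, however, shows an end-of-Visit-4 primary analysis with no matching section in the body; if that analysis is intended, Visit 5 would not be available for everyone and only items 1 and 3 apply in full.

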If there are missing mITT analysis set monocular DCNVA or DCIVA data at Visit 4, then missing data will be imputed using the Markov chain Monte Carlo multiple imputation method. After imputation of missing data, the statistical hypotheses will be tested using two-sided two-sample t-tests by imputation.

For each endpoint, an overall p-value resulting from the multiple imputation method will be estimated. The treatment effect (mean Test group IOL VA minus mean Control group IOL VA) in logMAR units will be summarized using continuous summary statistics and a two-sided 95% confidence interval. If the p-value from the multiple imputation analysis of treatment effect is less than or equal to 0.05 and the treatment effect is less than or equal to -0.10 logMAR units for DCIVA (i.e., the Test lens mean logMAR VA is at least 0.10 less than the mean for the control) or less than or equal to -0.20 logMAR units for DCNVA, then it will be concluded that the Test IOL is statistically and clinically successful in the corresponding outcome.

The previous continuous summary statistics will also be provided for the Per Protocol Set. However, superiority will not be evaluated with the PP Set, and statistical success will not depend upon the results of the PP analysis.

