## **13.2.2 Effectiveness Endpoints**

The statistical success of the trial will depend on the statistical success of all three primary effectiveness endpoints.

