### Second Primary Effectiveness Endpoint

For the second primary effectiveness endpoint, photopic monocular logMAR DCNVA in first eyes at Post-Operative Visit 4, the null and alternative hypotheses are as follows:

$$H_0: \mu_T = \mu_C$$

$$H_1: \mu_T \neq \mu_C$$

Where:

- $\mu_T$  = the mean logMAR DCNVA of the Test (trifocal) group, and
- $\mu_C$  = the mean logMAR DCNVA of the Control (monofocal) group

If the null hypothesis is rejected and the mean for the Test group is less than the mean for the Control group, then it will be concluded that the Test IOL is statistically successful in this outcome.

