#### **13.3.4 Primary Effectiveness Endpoints**

Approximately the first 24 evaluable Test group subjects and 12 evaluable Control group subjects will be excluded from the near and intermediate visual acuity hypothesis tests, leaving an expected evaluable sample size of approximately 276 Test group subjects and 138 Control group subjects to be included in the near and intermediate visual acuity hypothesis tests.

Regarding the non-inferiority test of BCDVA, when the sample sizes in the groups are 300 (Group 1) and 150 (Group 2), a two group 0.050 one-sided t-test will have 99% power to reject the null hypothesis that the Test and Control IOLs are not equivalent (the difference in means,  $\mu_T - \mu_S$ , is 0.10 or farther from zero in the same direction) in favor of the alternative hypothesis that the means of the two groups are equivalent, assuming that the expected difference in means is 0.00 and the common standard deviation is 0.15.

Regarding the comparisons of BCDVA to the ISO grid, ISO 11979-7 specifies a sample size of approximately 300 completed subjects for this type of investigation.

Regarding the superiority tests of DCNVA at 40 cm and DCIVA and 66 cm, a two-group t-test with a 0.05 two-sided significance level will have 99% power to detect a difference in means of -0.10, assuming that the common standard deviation is 0.15, when the sample sizes in the two groups are 276 and 138 subjects, respectively (a total sample size of 414 subjects).

Regarding the assessment of clinical superiority in DCNVA at 40 cm and DCIVA at 66 cm, the probability that the Test group’s mean logMAR VA will be at least 0.10 units less than the Control group’s mean logMAR VA will be 89% if the true difference is -0.12 units, 97% if the true difference is -0.13 units, and 99% if the true difference is -0.14 units, assuming that the common standard deviation is 0.15 when the sample sizes in the two groups are 276 and 138 subjects, respectively (a total sample size of 414 subjects).

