#### 13.5.3.2 Photopic Monocular DCNVA

Photopic monocular distance-corrected near visual acuity (DCNVA) at 40 cm in first eyes at Post-Operative Visit 4 will be summarized using continuous summary statistics in logMAR units by treatment assignment for the mITT Set Phase II and III subjects (combined). The DCNVA best distance data from the Phase I/Pilot subjects will be excluded from hypothesis testing and will be summarized separately from the data of the other subjects.

If there are missing mITT analysis set monocular DCNVA data at Visit 4, then missing data will be imputed using the Markov chain Monte Carlo (MCMC) multiple imputation method. After imputation of missing data, the statistical hypotheses will be tested using a statistical model with treatment and site as fixed factors by imputation.

An overall p-value resulting from the multiple imputation method will be estimated. The treatment effect (mean Test group IOL VA minus mean Control group IOL VA) in logMAR units will be summarized using continuous summary statistics and a two-sided 95% confidence interval. If the p-value from the multiple imputation analysis is less than or equal to 0.05 and the treatment effect is less than or equal to -0.20 (i.e., the Test lens mean logMAR VA is at least 0.20 less than the mean for the control), then it will be concluded that the Test IOL is statistically and clinically successful (i.e., superior to the Control IOL) in this outcome.

The previous continuous summary statistics will also be provided for the Per Protocol Set. However, superiority will not be evaluated with the PP Set and statistical success will not depend upon the results of the PP analysis.

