### **13.5.3.3 Photopic Monocular DCIVA**

Photopic monocular distance-corrected intermediate visual acuity (DCIVA) at 66 cm in first eyes at Post-Operative Visit 4 will be converted from letters correct to logMAR units using the method described above for BCDVA and summarized using continuous summary statistics in logMAR units by treatment assignment for the mITT Set Phase II and III subjects (combined). The DCIVA data from the Phase I/Pilot subjects will be excluded from hypothesis testing and will be summarized separately from the data of the other subjects.

If there are missing mITT analysis set monocular DCIVA data at Visit 4, then missing data will be imputed using the MCMC multiple imputation method. After imputation of missing data, the statistical hypotheses will be tested using a statistical model with treatment and site as fixed factors by imputation.

An overall p-value resulting from the multiple imputation method will be estimated. The treatment effect (mean Test group IOL VA minus mean Control group IOL VA) in logMAR units will be summarized using continuous summary statistics and a two-sided 95% confidence interval. If the p-value from the multiple imputation analysis is less than or equal to 0.05 and the treatment effect is less than or equal to -0.10 (i.e. the Test lens mean logMAR VA is at least 0.10 less than the mean for the control), then it will be concluded that the Test IOL is statistically and clinically successful (i.e., superior to control) in this outcome.

The previous continuous summary statistics will also be provided for the Per Protocol Set. However, superiority will not be evaluated with the PP Set and statistical success will not depend upon the results of the PP analysis

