6.4 Primary Effectiveness Endpoints

Approximately the first 24 evaluable Test group subjects and 12 evaluable Control group subjects will be excluded from the near and intermediate VA hypothesis tests, leaving an expected evaluable sample size of approximately 276 Test group subjects and 138 Control group subjects to be included in the near and intermediate visual acuity hypothesis tests.

Regarding the non-inferiority test of BCDVA, when the sample sizes in the groups are 300 (Group 1) and 150 (Group 2), a two group 0.050 one-sided t-test will have 99% power to reject the null hypothesis that the Test and Control IOLs are not equivalent (the difference in means, $\mu_T - \mu_S$, is 0.10 or farther from zero in the same direction) in favor of the alternative hypothesis that the means of the two groups are equivalent, assuming that the expected difference in means is 0.00 and the common SD is 0.15.

Regarding the comparisons of BCDVA to the ISO grid, ISO 11979-7 specifies a sample size of approximately 300 completed subjects for this type of investigation.

Regarding the superiority tests of DCNVA at 40 cm and DCIVA and 66 cm, a two-group t-test with a 0.05 two-sided significance level will have 99% power to detect a difference in means of -0.10, assuming that the common SD is 0.15, when the sample sizes in the two groups are 276 and 138 subjects, respectively (a total sample size of 414 subjects).

Regarding the assessment of clinical superiority in DCNVA at 40 cm and DCIVA at 66 cm, the probability that the Test group's mean logMAR VA will be at least 0.10 units less than the Control group's mean logMAR VA will be 89% if the true difference is -0.12 units, 97% if the true difference is -0.13 units, and 99% if the true difference is -0.14 units, assuming that the common standard deviation is 0.15 when the sample sizes in the two groups are 276 and 138 subjects, respectively (a total sample size of 414 subjects).

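### For co-primary DCNVA at 40 cm the protocol requires an observed effect of -0.20 logMAR or better and the SAP only -0.10, and the SAP does not log the difference

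*SAP*

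**What the plan says.** Protocol 13.5.3.2 makes the DCNVA conclusion depend on p of at most 0.05 and on an observed effect: "the treatment effect is less than or equal to -0.20 (i.e., the Test lens mean logMAR VA is at least 0.20 less" than Control. The synopsis (Primary Effectiveness Analyses) repeats it as "less than or equal to -0.20 logMAR units for DCNVA" and, in the same sentence, gives -0.10 for DCIVA. Protocol 13.5.3.3 confirms the DCIVA value: "the treatment effect is less than or equal to -0.10 (i.e. the Test lens mean logMAR VA is at least 0.10 less".

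SAP 13.3.2 uses nearly the same wording for DCNVA, but the condition is "the treatment effect is less than or equal to -0.10 (i.e., the Test lens mean logMAR VA is at least 0.10 less". SAP 13.3.3 refers back to 13.3.2, so DCIVA gets -0.10 as well.

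The SAP states that it supports protocol Version 8.0. Its Section 16 lists three changes from the protocol, all about the analysis population for safety endpoints.

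The sample-size text in both documents takes 0.10 as the clinical criterion for both endpoints. SAP 6.4 introduces it with "Regarding the assessment of clinical superiority in DCNVA at 40 cm and DCIVA at 66 cm". Protocol 13.3.4 says the probability of meeting it "will be 89% if the true difference is -0.12 units, 97% if the true difference is -0.13 units", and 99% at -0.14.

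On trial success, Protocol 13.2.2 and SAP 3.3.5 agree: "The statistical success of the trial will depend on the statistical success of all three primary effectiveness endpoints". The hypothesis text for DCNVA defines statistical success without any threshold: "If the null hypothesis is rejected and the mean for the Test group is less than the mean for the Control group".

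**The concern.** The two documents give different success rules for the same co-primary endpoint, at the same visit and distance. The SAP's rule is the more lenient, and nothing marks it as an intended change. A stray digit in the protocol is an unlikely explanation, because -0.20 appears there twice and is set apart from the DCIVA value both times. A slip in the SAP is not certain either, because the protocol's own sample-size text supports 0.10 for DCNVA.

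If this is left open, the sponsor could choose between two written rules for a superiority conclusion once the data are known. The plan also offers a third candidate, the direction-only definition in the hypothesis sections, and does not say which of the three defines success for the trial or opens testing of the secondary endpoints.

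**Working it through.** **Inputs.** Common SD 0.15; 276 Test and 138 Control subjects (Protocol 13.3.4, SAP 6.4). Two-sided 0.05 test. Thresholds -0.20 (Protocol 13.5.3.2, synopsis) and -0.10 (SAP 13.3.2). The check uses a normal approximation and ignores the site factor and the multiple imputation.

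**Standard error.** SE = 0.15 × √(1/276 + 1/138) = 0.01564.

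**The plan's own figures.** P(observed ≤ -0.10) = Φ((|true| - 0.10)/SE):

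- true -0.12: Φ(0.02/0.01564) = 90.0% (stated 89%)
- true -0.13: Φ(0.03/0.01564) = 97.2% (stated 97%)
- true -0.14: Φ(0.04/0.01564) = 99.5% (stated 99%)

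The stated figures are right for a 0.10 criterion. Neither document gives a figure for 0.20.

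**Does the p-value matter in the disputed range?** The smallest significant difference is t(0.975, 412 df) × SE = 0.0307. An observed -0.10 gives t = 0.10/0.01564 = 6.39, p about 4 × 10⁻¹⁰. The p-value condition is met throughout, so only the threshold separates the two rules.

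**Chance of a split conclusion.** P(split) = P(observed ≤ -0.10) - P(observed ≤ -0.20). The first three true effects are those the plan tabulates; the others are illustrative.

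| True effect | Meets SAP -0.10 | Meets protocol -0.20 | SAP yes, protocol no |
|---|---|---|---|
| -0.12 | 90.0% | <0.01% | 90.0% |
| -0.13 | 97.2% | <0.01% | 97.2% |
| -0.14 | 99.5% | <0.01% | 99.5% |
| -0.15 | 99.9% | 0.07% | 99.9% |
| -0.18 | >99.9% | 10.0% | 90.0% |
| -0.20 | >99.9% | 50.0% | 50.0% |
| -0.22 | >99.9% | 90.0% | 10.0% |
| -0.24 | >99.9% | 99.5% | 0.5% |

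Against -0.20, success probabilities of about 90%, 97% and 99% therefore need true effects of -0.22, -0.23 and -0.24.

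**Sensitivity to the SD.** At SD 0.20 (an assumption here; the documents use it for binocular DCNVA), SE = 0.02085. An observed -0.10 is still significant (p about 2 × 10⁻⁶). The split is 98% at -0.15, 83% at -0.18, 50% at -0.20 and 17% at -0.22.

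**Secondary endpoints.** Protocol 13.5.4 sends all four binocular endpoints to the DCNVA and DCIVA methods. SAP 13.4.2 and 13.4.4 refer back to 13.3.2, which on a plain reading brings -0.10 with it. SAP 13.4.1 and 13.4.3 state no threshold. The hypothesis sections (Protocol 13.2.2, SAP 3.3.6) give all four a rule based on rejection, direction and the preceding step only.

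**The case against.** The strongest counter-argument concerns how far the conflict reaches. Both documents define statistical success for DCNVA as rejection of the null with a lower Test mean. An effect between the two thresholds is therefore statistically successful under both; only the combined statistical-and-clinical conclusion differs. SAP 9.4 locates the primary success criteria in Section 3.3, which carries no DCNVA threshold, and entry to the secondary tests is worded in terms of statistical success. Within the SAP, the natural reading is that neither the trial verdict nor that entry condition depends on -0.10 or -0.20.

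This limits the claim: a reversal of the trial verdict is not shown. It does not remove the conflict. Protocol 13.6.3 points to Section 13.1 for the criteria, and that section lists endpoints without any, so the protocol leaves the matter open. The combined rule is also the one each analysis section uses to declare superiority in DCNVA, which the synopsis names as a primary effectiveness objective.

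Two smaller points also stand. The split probabilities are conditional on the true effect and do not forecast this trial's result. And the SAP compares least-squares means, whereas the protocol speaks of a difference in means (t-tests in the synopsis), so the statement that only the SAP rule can pass alone holds for one and the same estimate.

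**Conclusion.** The conflict is real, it is not logged, and no provision in the documents resolves it. For any observed DCNVA effect at or below -0.10 but above -0.20, the combined conclusion is success under the SAP and failure under the protocol; exactly -0.20 passes both. At SD 0.15 and 276/138 subjects, the split is close to certain for a true effect of -0.15, even odds at -0.20, and rare only from about -0.24. The documents support either value, so this review does not choose one. What follows for trial success and the secondary endpoints is undetermined, because the plan does not say whether success includes the threshold. The figures rest on the planned SD and sample sizes and a normal approximation; an SD of 0.20 does not change the picture. This must be fixed.

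**What to change.** Before unmasking:

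1. Set one DCNVA threshold in both documents. If it is -0.20, put it in SAP 13.3.2 and state -0.10 for DCIVA separately in 13.3.3, because 13.3.3 inherits whatever 13.3.2 says. If it is -0.10, amend the protocol synopsis and 13.5.3.2 and record the change in SAP Section 16.
2. Restate the DCNVA success probabilities in Protocol 13.3.4, the synopsis and SAP 6.4 at the chosen threshold. Keep the present figures for DCIVA.
3. In Protocol 13.2.2 and SAP 3.3.5, say whether trial success, and with it entry to the secondary tests, requires the threshold or only rejection in the right direction.
4. State the threshold, if any, for each of the four secondary endpoints.

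No additional subjects or measurements are needed. The edits are short, but they settle a co-primary decision rule. Keeping -0.20 makes the stated DCNVA success probability much lower for small true effects. Keeping -0.10 requires a protocol amendment and relaxes the protocol's written criterion.
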